12.2.2.4 Ultrasound

Ultrasound is not useful in assessment of lesion size and should not be used as a method of measurement. Ultrasound examinations cannot be reproduced in their entirety for independent review at a later date and, because they are operator dependent, it cannot be guaranteed that the same technique and measurements will be taken from one assessment to the next. If new lesions are identified by ultrasound in the course of the study, confirmation by CT or MRI is advised. If there is concern about radiation exposure at CT, MRI may be used instead of CT in selected instances.

12.2.2.5 PET-CT

If the site can document that the CT performed as part of a PET-CT is of identical diagnostic quality to a diagnostic CT (with IV and oral contrast), then the CT portion of the PET-CT can be used for RECIST measurements and can be used interchangeably with conventional CT in accurately measuring cancer lesions over time with approval from the Principal Investigator/designee.

12.2.2.6 FDG-PET

FDG-PET scanning is allowed to complement CT scanning in assessment of progressive disease (PD) and particularly possible new disease. A positive FDG-PET scanned lesion is defined as one which is FDG avid with an uptake greater than twice that of the surrounding tissue on the attenuation corrected image; otherwise, an FDG-PET scanned lesion is considered negative. New lesions on the basis of FDG-PET imaging can be identified according to the following algorithm:

- Negative FDG-PET at baseline, positive FDG-PET at follow-up: PD based on a new lesion.
- No FDG-PET at baseline, positive FDG-PET at follow-up: If the positive FDG-PET at

follow-up corresponds to a new site of disease confirmed by CT, this is PD. If the positive FDG-PET at follow-up is not confirmed as a new site of disease on CT, additional follow-up CT scans are needed to determine if there is truly progression occurring at that site (if so, the date of PD will be the date of the initial abnormal FDG-PET scan). If the positive FDG-PET at follow-up corresponds to a pre-existing site of disease on CT that is not progressing on the basis of the anatomic images, this is not PD.

- FDG-PET may be used to upgrade a response to a CR in a manner similar to a biopsy in cases where a residual radiographic abnormality is thought to represent fibrosis or scarring. The use of FDG-PET in this circumstance should be prospectively described in the protocol and supported by disease-specific medical literature for the indication. However, it must be acknowledged that both approaches may lead to false positive CR due to limitations of FDG-PET and biopsy resolution/sensitivity.

12.2.3 Additional Considerations

- Tumor markers alone cannot be used to assess response. If markers are initially above the upper normal limit, they must normalize for a participant to be considered in complete clinical response.
- The cytological confirmation of the neoplastic origin of any effusion that appears or worsens during treatment when the measurable tumor has met criteria for response or stable disease is mandatory to differentiate between response or stable disease (an effusion may be a side effect of the treatment) and progressive disease.
- Cytologic and histologic techniques can be used to differentiate between PR and CR in rare cases (e.g., residual lesions in tumor types such as germ cell tumors, where known residual benign tumors can remain).

12.3 Lesion Documentation

12.3.1 Target Lesions

12.3.1.1 Measurable Lesions

Up to a maximum of 5 lesions, representative of all involved organs, should be identified as “Target Lesions” and recorded and measured at baseline. These lesions can be non-nodal or nodal (as defined), where no more than 2 lesions are from the same organ and no more than 2 malignant nodal lesions are selected.

NOTE: If fewer than 5 target lesions and target lymph nodes are identified, there is no reason to perform additional studies beyond those specified in the protocol to discover new lesions.

Target lesions and target lymph nodes should be selected on the basis of their size, be representative of all involved sites of disease, but in addition should be those that lend themselves to reproducible repeated measurements. It may be the case that, on occasion, the largest lesion (or malignant lymph node) does not lend itself to reproducible measurements in which circumstance the next largest lesion (or malignant lymph node) which can be measured reproducibly should be selected.

12.3.1.2 Baseline Sum of Diameters (BSD)

A sum of the longest diameter for all target lesions plus the sum of the short axis of all the target lymph nodes will be calculated and reported as the baseline sum of dimensions (BSD). The BSD will be used as reference to further characterize any objective tumor response in the measurable dimension of the disease.

12.3.1.3 Post-Baseline Sum of the Diameters (PBSD)

A sum of the longest diameter for all target lesions plus the sum of the short axis of all the target lymph nodes will be calculated and reported as the post-baseline sum of dimensions (PBSD). If the radiologist is able to provide an actual measurement for the target lesion (or target lymph node), that should be recorded, even if it is below 0.5 cm. If the target lesion (or target lymph node) is believed to be present and is faintly seen but too small to measure, a default value of 0.5 cm should be assigned. If it is the opinion of the radiologist that the target lesion or target lymph node has likely disappeared, the measurement should be recorded as 0 cm.

12.3.1.4 Minimum Sum of Diameters (MSD)

The minimum sum of the diameters (MSD) is the minimum of the BSD and the PBSD.

12.3.2 Non-Target Lesions & Non-Target Lymph Nodes

Non-measurable sites of disease including any measurable lesions over and above the 5 target lesions should be identified as non-target lesions or non-target lymph nodes and should also be recorded at baseline. Measurements of these lesions are not required, but the presence, absence, or in rare cases unequivocal progression of each should be noted throughout follow-up.

12.4 Response Criteria

12.4.1 Overview

All target lesions, as well as non-target lesions must be measured at the evaluation time points specified in the study calendar. Specifically, a change in objective status to either a PR or CR cannot be done without re-measuring target lesions and target lymph nodes.

NOTE: Non-target lesions and non-target lymph nodes should be evaluated at each assessment, especially in the case of first response or confirmation of response. In selected circumstances, certain non-target organs may be evaluated less frequently. For example, bone scans may need to be repeated only when complete response is identified in target disease or when progression in bone is suspected.

12.4.2 Evaluation of Target Lesions

12.4.2.1 Complete Response (CR)

Disappearance of all target lesions. Any pathological lymph nodes (whether target or non-target) must have reduction in short axis to < 10 mm.

12.4.2.2 Partial Response (PR)

At least a 30% decrease in the sum of the diameters of target lesions, taking as reference the baseline sum diameters.

12.4.2.3 Progressive Disease (PD)

At least a 20% increase in the sum of the diameters of target lesions, taking as reference the smallest sum on study (this includes the baseline sum if that is the smallest on study). In addition to the relative increase of 20%, the sum must also demonstrate an absolute increase of at least 5 mm.

NOTE: The appearance of one or more new lesions is also considered progression.

12.4.2.4 Stable Disease (SD)

Neither sufficient shrinkage to qualify for PR nor sufficient increase to qualify for PD, taking as reference the smallest sum diameters while on study.

12.4.3 Evaluation of Non-Target Lesions & Non-Target Lymph Nodes

12.4.3.1 Complete Response (CR)

Disappearance of all non-target lesions and normalization of tumor marker level. All lymph nodes must be non-pathological in size (< 10 mm short axis).

NOTE: If tumor markers are initially above the upper normal limit, they must normalize for a subject to be considered in complete clinical response.

12.4.3.2 Non-CR/Non-PD

Persistence of one or more non-target lesion(s) and/or maintenance of tumor marker level above the normal limits.

12.4.3.3 Progressive Disease (PD)

Appearance of one or more new lesions and/or *unequivocal progression* of existing non-target lesions. Unequivocal progression should not normally trump target lesion status. It must be representative of overall disease status change, not a single lesion increase.

NOTE: To achieve unequivocal progression on the basis of non-target disease, there must be an overall level of substantial worsening in non-target disease such that, even in presence of CR, PR or SD in target disease, the overall tumor burden has increased sufficiently to merit discontinuation of therapy. A modest increase in the size of one or more non-target lesions is usually not sufficient to qualify for unequivocal progression status. The designation of overall progression solely on the basis of change in non-target disease in the face of CR, PR or SD of target disease is therefore expected to be rare. In order for a PD to be assigned on the basis of non-target lesions, the increase in the extent of the disease must be substantial even in cases where there is no measurable disease at baseline. If there is unequivocal progression of non-target lesion(s), then at least one of the non-target lesions must be assigned a status of "Worsened." Where possible, similar rules to those described above for target lesions for assigning PD following a CR for the non-target lesion response in the presence of non-target lesions nodal lesions should be applied.

12.4.4 Symptomatic Deterioration

Participants with global deterioration of health status requiring discontinuation of treatment without objective evidence of disease progression at that time, and not either related to study treatment or other medical conditions, should be reported as PD due to "symptomatic deterioration." Every effort should be made to document the objective progression even after

discontinuation of treatment due to symptomatic deterioration. A participant is classified as having PD due to symptomatic deterioration if any of the following occur that are not either related to study treatment or other medical conditions:

- Weight loss > 10% of body weight
- Worsening of tumor-related symptoms
- Decline in performance status of > 1 level on ECOG scale

12.4.5 Evaluation of Best Overall Response

The best overall response is the best response recorded from the start of study treatment until disease progression/recurrence (taking as reference for progressive disease the smallest measurements recorded since the treatment started). The participant's best response assignment will depend on the achievement of both measurement and confirmation criteria.

For participants with measurable disease at baseline:

Target Lesions	Non-Target Lesions	New Lesions	Overall Response
CR	CR	No	CR
CR	Non-CR/ Non-PD	No	PR
CR	Not evaluated	No	PR
PR	Non-PD or not all evaluated	No	PR
SD	Non-PD or not all evaluated	No	SD
Not all evaluated	Non-PD	No	Non-evaluable
PD	Any	Yes or No	PD
Any	PD*	Yes or No	PD
Any	Any	Yes	PD

*In exceptional circumstances, unequivocal progression in non-target lesions may be accepted as disease progression.

For participants with non-measurable/evaluable disease only at baseline:

Non-Target Lesions	New Lesions	Overall Response
CR	No	CR
Non-CR/Non-PD	No	Non-CR/Non-PD
UNK/Not All Evaluated	No	Indeterminate
Unequivocal progression	Yes or No	PD
Any	Yes	PD

In some circumstances, it may be difficult to distinguish residual disease from normal tissue. When the evaluation of complete response depends on this determination, it is recommended that the residual lesion be investigated (fine needle aspirate/biopsy) to confirm the complete response status.

12.4.6 Progression-Free Survival

Progression-free survival (PFS) is defined as the time from the initiation of the study treatment until the date of objective disease progression or death (by any cause in the absence of

progression).

12.4.7 Response Review

There is no independent or central review of the radiology assessments planned for this trial. It is the responsibility of each participating site's Principal Investigator to ensure that tumor assessments are reported per the RECIST 1.1 criteria outlined above. The Principal Investigator (or designee) may choose to review select cases.

12.4.8 Confirmatory Measurement/Duration of Response

12.4.8.1 Confirmation of Response

To be assigned a status of PR or CR, changes in tumor measurements must be confirmed by repeat assessments performed no less than 4 weeks after the criteria for response are first met.

12.4.8.2 Duration of Overall Response

The duration of overall response is measured from the time measurement criteria are met for CR or PR (whichever is first recorded) until the first date that recurrent or progressive disease is objectively documented (taking as reference for progressive disease the smallest measurements recorded since the treatment started).

The duration of overall CR is measured from the time measurement criteria are first met for CR until the first date that progressive disease is objectively documented.

12.4.8.3 Duration of Stable Disease

The duration of SD is measured from the start of the treatment until the criteria for progression are met, taking as reference the smallest measurements recorded since the treatment started, including the baseline measurements.

13. ADVERSE EVENT REPORTING REQUIREMENTS

13.1 General

Adverse event collection and reporting is a routine part of every clinical trial. This study will use the descriptions and grading scales found in the NCI Common Terminology Criteria for Adverse Events version (CTCAE v5.0) that is available at

http://ctep.cancer.gov/protocolDevelopment/electronic_applications/ctc.htm.

Information on all adverse events, whether reported by the participant, directly observed, or detected by physical examination, laboratory test or other means, will be collected, recorded, followed and reported as described in the following sections.

Adverse events experienced by participants will be collected and reported from initiation of study medication, throughout the study, and within 30 days of the last dose of study medication. Participants who experience an ongoing adverse event related to a study procedure and/or study medication beyond 30 days will continue to be contacted by a member of the study team until the event is resolved, stabilized, or determined to be irreversible by the participating investigator. Participants should be instructed to report any serious post-study event(s) that might reasonably be related to participation in this study. The investigator should notify the IRB and any other

applicable regulatory agency of any unanticipated death or adverse event occurring after a participant has discontinued or terminated study participation that may reasonably be related to the study.

13.2 Definitions

13.2.1 Adverse Event (AE)

An adverse event is any undesirable sign, symptom or medical condition or experience that develops or worsens in severity after starting the first dose of study treatment or any procedure specified in the protocol, even if the event is not considered to be related to the study.

Abnormal laboratory values or diagnostic test results constitute adverse events only if they induce clinical signs or symptoms or require treatment or further diagnostic tests.

13.2.1.1 Suspected Adverse Reaction

Suspected adverse reactions are the subset of all adverse events for which there is a “reasonable possibility” (i.e., there is evidence to suggest a causal relationship between the drug and the adverse event) that the drug caused the event.

13.2.2 Serious Adverse Event (SAE)

A serious adverse event is an undesirable sign, symptom, or medical condition which:

- is fatal;
- is life-threatening (immediate risk of death);
- requires or prolongs inpatient hospitalization for ≥ 24 hours;
- results in persistent or significant disability/incapacity to conduct normal life functions;
- constitutes a congenital anomaly or birth defect; or
- Important Medical Events (IME) that may not result in death, be life threatening, or require hospitalization may be considered serious when, based upon medical judgment, they may jeopardize the patient or subject and may require medical or surgical intervention to prevent one of the outcomes listed in this definition.

Events **not** considered to be serious adverse events are hospitalizations for:

- routine treatment or monitoring of the studied indication, not associated with any deterioration in condition, or for elective procedures
- elective or pre-planned treatment for a pre-existing condition that did not worsen, or that is required per protocol
- emergency outpatient treatment for an event not fulfilling the serious criteria outlined above and not resulting in inpatient admission
- respite care
- Death due to disease progression unless attributable to the study treatment

Events listed above may be reported to a participating site’s local IRB, if required per local regulations.

13.2.3 Expectedness

Expected: Expected adverse events are those that have been previously identified as resulting from administration of the agent. For the purposes of this study, AEs are considered “expected”

if they are included in the *Reference Safety Information* section of the most current version of the sitravatinib Investigator's Brochure.

Unexpected: An adverse event is considered unexpected when it is not included, or varies in nature, intensity or frequency, from information provided in the *Reference Safety Information* section of the most current version of the sitravatinib Investigator's Brochure.

13.2.4 Attribution

Attribution is the relationship between an adverse event and the study treatment. Attribution will be assigned as follows:

- **Unrelated:** The adverse event is clearly unrelated to the study treatment.
- **Unlikely:** The adverse event is unlikely to be related to the study treatment.
- **Possibly:** The adverse event is possibly related to the study treatment.
- **Probably:** The adverse event is probably related to the study treatment.
- **Definite:** The adverse event is clearly related to the study treatment.

13.3 Reporting Procedures

13.3.1 General

All adverse events will be recorded on study-specific case report forms (CRFs).

13.3.2 Serious Adverse Events

All serious adverse events, regardless of causality to study drug, will be reported to the Principal Investigator and/or the Study Coordinator. Information pertaining to the SAE should be compiled on the Form FDA 3500A – MedWatch Mandatory Reporting (available on the FDA website). The Principal Investigator or designee should review the information in this report, along with any supporting documentation, and make a determination of causality. The Principal Investigator or designee should also review any follow-up information as it becomes available to determine if the causality assessment has changed.

13.3.3 Suspected, Unexpected Serious Adverse Reactions (SUSARs)

The Principal Investigator or designee must report any suspected adverse reaction to study treatment that is both serious and unexpected to the FDA via an IND safety report no later than 15 calendar days after determining that the information qualifies for reporting. Any unexpected fatal, or life-threatening, suspected adverse reactions must be reported to the FDA no later than 7 calendar days after initial receipt of the information.

13.3.4 Institutional Review Board (IRB)

Adverse events requiring modifications to the protocol and/or informed consent will be reported to the IRB. These modifications will be provided to the IRB with the report of the adverse event.

13.3.5 Food and Drug Administration (FDA)

The Dan L. Duncan Cancer Center at Baylor College of Medicine (DLDCC-BCM) has been designated as the Coordinating Center to manage the Investigational New Drug Application

(IND) associated with this protocol. The Coordinating Center and/or CRO will cross-reference this submission to Mirati Therapeutics' parent IND at the time of submission. Additionally, the Coordinating Center will submit a copy of these documents to Mirati Therapeutics at the time of submission to FDA.

The Coordinating Center will be responsible for all communication with the FDA in accordance with 21 CFR Part 312, which includes but is not limited to the 7- and 15-Day Safety Reports, as well as an Annual Progress Report. Additionally, the Coordinating Center will submit a copy of these reports to Mirati Therapeutics at the time of submission to FDA.

13.3.6 Mirati Therapeutics, Inc.

Mirati Therapeutics' procedure for SUSAR exchange is outlined below. All exchange of processed data will be by Form FDA 3500A – MedWatch. The narratives must contain assessments of expectedness and causality for all SAEs. Non-SUSAR SAEs are not routinely exchanged.

13.3.6.1 From Coordinating Center to Mirati Therapeutics

The Coordinating Center will forward Suspected Unexpected Serious Adverse Reactions (SUSARs) occurring on study with sitravatinib as follows:

- Reports of fatal or life threatening Serious Adverse Drug Reactions will be forwarded within three (3) calendar days of receipt date.
- Reports of Serious Adverse Drug Reactions (other than fatal or life threatening) will be forwarded within eight (8) calendar days of receipt date.

14. DATA AND SAFETY MONITORING

14.1 Data Management and Reporting

All participants who received any amount of study drug will be included in the safety analysis. Participants will be monitored at each clinic visit and at any other contact throughout the study for the occurrence of AEs and SAEs. The investigator and/or site staff will inquire about the occurrence of AEs/SAEs at every clinic visit or contact during the study. Adverse events will be graded according to the NCI Common Terminology Criteria v. 5.0 (CTCAEv5). All AEs/SAEs that occur during active treatment will be recorded in source documents and on CRFs, regardless

of grade or relationship to study treatment. Non-serious adverse events that occur during the 30-day follow-up period will only be recorded on the CRFs if the investigator believes there to be a possible relationship to study treatment. Serious adverse events occurring during the 30-day follow-up period should be recorded on the CRFs, regardless of suspected relationship to study treatment.

Safety analyses will include summaries of adverse event rates (both frequency and incidence tables), baseline laboratory parameters and changes from baseline, frequency of CTC toxicity grades for both laboratory and non-laboratory data. The investigators and others responsible for patient care at individual sites should institute any supplementary investigations of major adverse events based on their clinical judgment of the likely causative factors.

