3.2 Secondary Objectives

- 3.2.1 To evaluate Time to Progression (TTP), defined as the duration of time from initiation of treatment until progression according to RECIST 1.1 criteria
- 3.2.2 To evaluate Objective Response Rate (ORR), defined as the proportion of participants who achieve a Complete Response (CR) or Partial Response (PR) to treatment per RECIST 1.1 criteria
- 3.2.3 To evaluate the Clinical Benefit Rate (CBR), defined as the proportion of participants who achieve CR, PR, or stable disease (SD) per RECIST 1.1 criteria
- 3.2.4 To evaluate the number of participants with grade 3 or higher adverse events as per the NCI Common Terminology Criteria for Adverse Events version 5.0 (CTCAEv5)

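### Sections 13.3.1 and 14.1 disagree on whether unrelated non-serious adverse events after the last dose go on the CRF, which leaves a small one-directional gap in the grade 3 or higher AE count

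*Combined protocol and SAP*

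**What the plan says.** Section 14.1 sets three recording rules.

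- On treatment: "All AEs/SAEs that occur during active treatment will be recorded in source documents and on CRFs, regardless" of grade or relationship.
- Serious events after treatment: "Serious adverse events occurring during the 30-day follow-up period should be recorded on the CRFs, regardless of suspected relationship to study treatment".
- Non-serious events in the 30-day follow-up: these "will only be recorded on the CRFs if the investigator believes there to be a possible relationship to study treatment". There is no exception for non-serious events of grade 3 or higher.

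Section 13.3.1 states: "All adverse events will be recorded on study-specific case report forms (CRFs"), with no carve-out. Section 13.1 runs collection and reporting from the start of study medication, "throughout the study, and within 30 days of the last dose of study medication". It uses relationship to treatment only to decide who is contacted later: "Participants who experience an ongoing adverse event related to a study procedure and/or study medication beyond 30 days". Section 13.1 also says that information on all events "will be collected, recorded, followed and reported as described in the following sections".

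Secondary objective 3.2.4 reads "To evaluate the number of participants with grade 3 or higher adverse events", graded by CTCAE version 5.0, and 16.5.2 plans to summarise that number. Neither section gives an attribution condition or a collection window. The AE definition in 13.2.1 does not depend on relationship to the study.

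**The concern.** The endpoint is written without reference to cause, and the data feeding it are complete on that basis only while the participant is on treatment. After the last dose, a non-serious grade 3 event that the investigator rates unrelated or unlikely need not reach the CRF. The same event shortly before the last dose would be counted.

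Grade and seriousness are different scales. Section 13.2.2 defines seriousness by outcome (death, threat to life, hospitalisation and so on), so the protection that 14.1 gives to SAEs does not cover every grade 3 event.

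Two things are at stake. First, sites that follow 13.3.1 and sites that follow 14.1 will submit different data. Second, the grade 3 or higher count can only be too low, and the attribution summary planned in 16.5.2 will lack the unrelated and unlikely non-serious events of the post-treatment period.

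**Working it through.** The plan states no figure on this point, so there is none to reproduce. The check is a comparison of the texts, followed by an illustration of size.

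**1. One event under each section.** Take a non-serious grade 3 event, rated unlikely to be related, that starts within 30 days after the last dose.

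| Section | Treatment of the event |
|---|---|
| 13.1 | Within the collection window; relationship matters only for contact beyond 30 days |
| 13.3.1 | Goes on the CRF |
| 14.1 | Does not go on the CRF |
| 3.2.4, 16.5.2 | No attribution condition that would exclude it; no window stated |

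The conflict between 13.3.1 and 14.1 is direct. The conflict with 13.1 is softer, because 13.1 defers to later sections and 14.1 is one of them. Section 13.3.1 is also a later section, however, and nothing says which governs.

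**2. Who drops out of the count.** A participant is missed only if all of these hold: no grade 3 or higher event on treatment; a first such event in the 30-day follow-up; that event is non-serious; and it is considered not even possibly related.

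**3. Size.** Let p be the probability of a grade 3 or higher event on treatment. Let q be the probability that a participant without one has a missed first event as in step 2.

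Undercount in the rate = (1 − p) × q. Expected participants missed of 25 = 25 × (1 − p) × q.

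Inputs:
- p = 485/1,106 = 0.439, from section 4.3 (sitravatinib-related grade 3 events, all studies combined). It is a stand-in for p.
- q is not in the documents. It is assumed at 2%, 5% and 10%.
- 25 is the maximum number of PFS24-evaluable participants (16.3). The safety population may be larger, because 16.6 replaces inevaluable participants.

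| q (assumed) | (1 − 0.439) × q | Of 25 participants |
|---|---|---|
| 2% | 1.1 percentage points | 0.3 |
| 5% | 2.8 percentage points | 0.7 |
| 10% | 5.6 percentage points | 1.4 |

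The stand-in for p counts related events only. An all-cause p in the same subjects would be at least as high and would shrink these figures. Shorter treatment in this population could lower p, but even at p = 0 the expected number is 25q, or 0.5 to 2.5.

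**4. Share of observation time.** This shows how much of the AE window the filtered period occupies. It does not measure lost events. Assume exponential PFS with 24-week rate r, so S(t) = r^(t/24).

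- r = 3% (unacceptable rate, 16.3): S(8 weeks) = 0.03^(8/24) = 0.311, so 69% have had a PFS event by the first scan. For a participant stopping at day 56: 30/(56 + 30) = 35%.
- r = 30% (target rate in PTPN12-low): median = 24 × ln 0.5 / ln 0.30 = 13.8 weeks, about 97 days; 30/(97 + 30) = 24%.
- A participant treated for the full 24 weeks: 30/(168 + 30) = 15%.

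**The case against.** The best defence is that 14.1 is the specific rule and 13.3.1 a one-line general statement naming the recording instrument. On that reading 14.1 governs, and limiting post-treatment entries to related events is an accepted way to reduce burden. Treatment stops at progression, so later unrelated events may reflect the cancer or the next therapy. This has force as a design preference. It does not remove the literal conflict, and it does not tell the reader of 3.2.4 that the count follows the narrower rule.

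A reader might infer several stronger things that the documents do not support.

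- *The endpoint's definition changes partway.* The written definition stays the same and states no window; what changes is which events are captured.
- *A third of the safety data is lost.* The 35% is a share of observation time under the unacceptable PFS rate. Only events meeting every condition in step 2 are affected.
- *Known drug effects would vanish.* Hypertension, diarrhoea and fatigue are the leading related grade 3 events in section 4.3, so they are likely to pass a threshold of merely possible relationship. With a half-life of 43 to 58 hours, day 30 (720 hours) is about 12 to 17 half-lives out, so a late unlikely rating may also be right.
- *The events are irrecoverable.* Section 14.1 limits CRF entry and does not bar source documentation. Adverse events are assessed at the 30–45 day contact (7.3.2), and 14.2 has the Principal Investigator review all of them.

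The absence of blinding and of a control arm affects every attribution in this trial, so it is not a defect particular to this rule.

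**Conclusion.** The point holds as an inconsistency in recording rules that bears on a named secondary endpoint. Section 14.1 contradicts 13.3.1 directly and 13.1 more softly. If 14.1 is followed, the grade 3 or higher count is complete on treatment and filtered by attribution afterwards for non-serious events, so any error is an undercount.

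The effect is probably small. The estimate of about 0.3 to 1.4 of 25 participants rests wholly on the assumed q of 2% to 10% and on a pooled related-event rate standing in for p. PFS24, the decision rules and the power statement do not use these data and are unaffected. The case for changing the text is that the gap runs one way and costs very little to close.

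**What to change.** - **14.1:** record all grade 3 or higher AEs and all SAEs through 30 days after the last dose regardless of attribution. Keep the relatedness filter only for non-serious grade 1–2 events in that period.
- **Data items:** record attribution and the start date of any new anticancer therapy, so that events possibly due to progression or subsequent treatment can be summarised separately.
- **13.1 and 13.3.1:** align both with the revised 14.1.
- **3.2.4 and 16.5.2:** state that the count runs from first dose to 30 days after the last dose, whatever the attribution.

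The safety contact at 30–45 days already asks about adverse events, so no visit is added. The cost is a few more CRF lines and a slightly higher reported count, some of which may reflect progression or the next therapy. If the sponsor prefers to keep the present filter, the minimum is to write the exception into 13.3.1 and to say in 3.2.4 and 16.5.2 that the count is restricted after the last dose.
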